7.7.4. Time for inclusion in the study

A subject is considered to be included in the study when the consent form is signed by both the subject and the study staff.

7.7.5. Expected total time required for the clinical study

The study is expected to start in August 2015 and end in November 2016, ie a total of 16 months. Recruitment of study participants is estimated to last for 4 months and each study participant is followed for 12 months.

7.7.6. Expected total time required for the individual subject's participation

The first visit is estimated to take about 1 hour. The following visit takes about half an hour.

7.7.7. Number of subjects to be included in the study

A total of 106 patients are expected to be included in the study, divided 1: 1 between control arm and TripleA arm.

7.7.8. Estimated time required to include this number of subjects

The recruitment period is estimated to last 4 months.

7.8. Procedures

7.8.1. Case Report Form (CRF)

In connection with each visit, the study staff must fill in the relevant section of the CRF and update the ongoing logs that follow the patient during the study.

7.8.2. Visit 1

- Obtaining informed consent (see also section 17)
- Control of inclusion and exclusion criteria (see sections 8.7.1 and 8.7.2)
- Baseline data that reflects the initial position before the patient begins the current care contact, i.e. before enrolling in the alcohol program. At visit 1, the study participants need to answer the following form with the period before enrollment in mind.
 - o SADD see section 8.3.1 above and Appendix B
 - o TLFB see sections 8.1.2 and 8.3.2 above and Appendix C
 - o AUDIT see section 8.3.3 above and Appendix D
- If this data is available from a time representative of Baseline, and has been obtained as part of a regular routine before the patient signs the informed consent to participate in the current study, the forms do not need to be filled in again.
- General history and medical examination (medical, neurological and psychiatric) and consequences of alcohol dependence on the patient's cognitive, psychological and physiological functions. In particular, lung function should be considered, given the ability to use TripleA.
- Demographic data are noted in the CRF

- o age
- o sex
- o weight
- o socio-economic factors
 - Beverage history is noted in CRF
- o Age when drinking began
- o Number of years of heavy drinking
- o Age when addiction began
- o Episodic or chronic drinking
- o previous attempts to remain sober, how long the period of sobriety was and what treatment was used
 - DUDIT (Drug Use Disorders Identification Test) See section 8.3.4 and Appendix E
 - CGI Severity (Clinical Global Impression Severity Score) is noted in CRF, see section 8.3.6
 - EQ-5D: See Section 8.3.7 and Appendix G
 - Documentation of the goal that the patient and the care provider have agreed on (controlled drinking or total sobriety) See Appendix F Motivation questions.
 - Blood samples are taken (see section 8.3.8)
 - Urine test for drug screening (see section 8.7.3)
 - Assessment phase and / or Conventional treatment is documented in CRF
 - Randomization to one of the treatment arms takes place by the care provider identifying the next available patient number on its list. The patient numbers must be distributed consecutively and for each patient number there is a code envelope that the care provider opens to find out whether the patient should participate in the control arm or use TripleA.

If the patient is randomized to TripleA:

- Distribution of TripleA
- Registration of the patient in the care provider portal.
- The patient is instructed on how to use TripleA and may practice using the equipment under the supervision of the study staff before taking the equipment home.
 - If any incidents with TripleA occur during the visit, these must be reported (see section 18 Safety reporting)

Note that the assigned device number must be registered both in the care provider portal and on a separate list of study equipment.

The source text is required if you want further information about the translation

[Send feedback](#)

[Side panels](#)

7.8.3.Before all the following visits:

7.8.3.1. Checking patient status in the caregiver portal (TripleA arm only).

Prior to each study visit, the study staff checks the patient's status in the care provider portal with regard to

- If completed blows were performed by the right person (ID check via photo).
- If completed blows indicate alcohol intake or not.
- Participation in agreed meetings (if applicable).

7.8.3.2. Measures in the event of noted deviations in the care provider portal

Deviations in the form of a positive or missed sobriety test must be discussed with the patient at the visit and allowed to influence the TLFB responses.

The caregiver has the opportunity to enter status comments for an individual test, which means that the database will contain supplementary information - without overwriting the basic status. The following options are available:

If the basic status is "Missed", the following status comments can be selected:

- No alcohol
- Alcohol could not be excluded
- Technical issue.

If the default status is "Alcohol could not be excluded", the following status comments can be selected:

- No alcohol
- Technical issue.

If the basic status is "Technical error", the following status comments can be selected:

- No alcohol
- Alcohol could not be excluded

7.8.3.3. Measures in case of detected relapses (regardless of information source)

The normal process when patients have relapsed is followed, which means that for each individual is discussed and decided what is best in the current situation - whether it is relevant to change something in the treatment, work with motivation or management of triggers. If necessary, MI, relapse prevention and / or medication are offered.

7.8.4. Visit 2 (Follow-up after 1 month)

- TLFB - See section 8.3.2 and Appendix C.
- Blood test - See section 8.3.8.
- Note changes in medication and other conventional treatment. Update relevant assessment phase information (WP2 only) - See sections 8.3.9 and 8.3.10
- Compliance - See section 8.3.12
- Safety reporting - See section 18

7.8.5. Visit 3 (Follow-up after 2 months)

- TLFB - See section 8.3.2 and Appendix C.
- Blood test - See section 8.3.8.
- Note changes in medication and other conventional treatment. Update assessment phase information if relevant - See sections 8.3.9 and 8.3.10
- Compliance - See section 8.3.12
- Safety reporting - See section 18

7.8.6. Visit 4 (Follow-up after 3 months)

- TLFB - See section 8.3.2 and Appendix C.
- Blood test - See section 8.3.8.
- Note changes in medication and other conventional treatment. Update the assessment phase information if relevant - See sections 8.3.9 and 8.3.10
- Compliance - See section 8.3.12
- Safety reporting - See section 18

7.8.7. Visit 5 (Follow up after 6 months)

- TLFB - See section 8.3.2 and Appendix C.
- Blood test - See section 8.3.8
- AUDIT - See section 8.3.3 above and Appendix D
- CGI Improvement Scale (Clinical Global Impression Severity Score): See section 8.3.6
- EQ-5D: See Section 8.3.7 and Appendix G
- SADD: See section 8.3.1 and Appendix B
- Note changes in medication and other conventional treatment - See section 8.3.10
- Compliance - See section 8.3.12
- Safety reporting - See section 18
- Check that the patient has had a new TripleA device sent home and returned the old one for calibration

7.8.8. Visit 6 (Close-out visit after 12 months)

- TLFB - See section 8.3.2 and Appendix C.
- Blood test - See section 8.3.8
- AUDIT - See section 8.3.3 above and Appendix D
- CGI Improvement Scale (Clinical Global Impression Severity Score): See section 8.3.6
- EQ-5D: See Section 8.3.7 and Appendix G
- SADD: See section 8.3.1 and Appendix B
- Note changes in medication and other conventional treatment - See section 8.3.10
- Compliance - See section 8.3.12
- Safety reporting - See section 18
- Return of TripleA.
- End the patient in the caregiver portal

7.8.9. Follow up and treatment after the study

The caregiver decides how the patient should be followed up and possibly treated after the end of the study. Any continued use of TripleA takes place within the framework of ordinary care.

7.8.10. Sponsors activities

Kontigo Care performs calibration of equipment and technical support for TripleA.

7.8.11. Factors that can affect the result

How motivated the patient is to abstain from alcohol will have an impact on whether one succeeds in abstaining from drinking alcohol during the course of the study. However, in order to make a study as realistic as possible, patients will not be selected depending on how motivated they are.

On the other hand, motivational factors will be mapped (see Appendix F) and thus you can get information on whether the degree of motivation in the two treatment groups is comparable or not, and whether it is possible to link the degree of motivation to the treatment result. The degree of severity of the dependence and the possible impact of demographic and social factors on the result will also be taken into account with exploratory analyzes.

The trust between therapist and patient can be of great importance for the treatment result and even if the methodology applied by the therapists is the same, it is conceivable that it matters which therapist you meet. Therefore, the randomization procedure will ensure that each therapist treats patients in both treatment arms to the greatest possible extent.

The treatment the patient receives may play a role in how the patient succeeds, but there is a lack of unambiguous data that suggests that a certain treatment works better than others, both in general and for specific patient groups. We therefore allow a wide range of treatment methods as background treatment in the clinical studies with TripleA. Descriptive statistics will be presented for what the distribution of treatment methods looks like in the various treatment arms. The patient material in the current study is probably too small to be able to draw any conclusions as to whether any treatment works better or worse in combination with TripleA, but exploratory subgroup analyzes will be performed.

The efficacy measures based on self-reported TLFB data may be affected if patients provide incorrect information in an attempt to protect their addiction and to conceal their possible drinking. In this study, the probability of a recurrence being detected is lower in the control arm than in the TripleA arm. This risks giving an incorrect comparison as frequent measurements in the TripleA arm (at least 3 times a day) increase the possibility of detecting the use of alcohol, which would otherwise have gone unnoticed. TLFB data can also be affected and provide more honest reporting as the patient knows that even shorter relapses risk being detected through the frequent alcohol tests. This could mean that even if the actual alcohol use in the TripleA arm is lower than in the control arm, we get more reports of alcohol use in the TripleA arm.

However, it is reasonable to assume that even if more alcohol intake is detected with TripleA, the actual alcohol intake pattern is not worse in the TripleA arm than in the control arm. It is also an advantage that relapses and alcohol intake become clear to both the patient and the therapist, in order to be able to work with relapses and the factors that trigger them within the framework of the treatment. The earlier you can stop a risky alcohol intake, the less the consequences for both the patient and the environment.

Although more relapses would be detected in the TripleA arm due to the frequent measurements, there is a possibility that the support that the system provides to maintain sobriety leads to more patients completing the entire treatment and participating in aftercare throughout the study period. Our hypothesis is therefore that the proportion of patients without heavy drinking days is more and the proportion who carry out the entire aftercare is more in the arm where the care and aftercare has been strengthened with TripleA.

When the study was designed, it was considered within the framework of the study to carry out more frequent checks of biomarkers to get a "real" result also for the control arm's alcohol intake, but the choice was made not to introduce more frequent biomarker controls (which in itself can have a deterrent effect on alcohol intake, to the price of further restrictions in the patient's daily life and increased costs for laboratory analyzes). One of the reasons for this choice is that the results of the study should be able to be compared with the interventions the patients currently receive.

8. Monitoring plan

The planned monitoring of the study, including verification of source data, is described in a separate monitoring plan.

9. Statistical considerations

9.1. Statistical design, method and analysis procedure

9.1.1. General

Continuous data will be summarized using descriptive statistics where the following parameters will be reported: number of observations, number of missing observations, mean, standard deviation, median, minimum and maximum. Categorical data will be presented with number (n) and percentage (%).

In addition to evaluation of all study data from the entire study period (12 months), 6-month data will also be evaluated.

Factors such as gender, severity of addiction, motivation, form of therapy and socio-economic factors will be considered as covariates in the statistical analyzes.

9.1.2. Efficacy evaluation

9.1.2.1. Primary efficacy endpoint

Proportion of patients who do not have heavy drinking days. A logistic regression model will be used to compare the groups.

Clinically relevant for treatment focused on risk reduction is that patients do not have heavy drinking days. The measurement tool will be TLFB (see Appendix C) where the number of days with large consumption over a four-week period is calculated.

Heavy drinking days are the same as days with heavy consumption, which means consumption of 4 or more standard glasses of alcohol per day for women and 5 or more standard glasses of alcohol per day for men. How to determine the TLFB at baseline is stated in section 8.1.2. Follow-up TLFB is then made at each visit.

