7.1.3. Measures taken to minimize or avoid bias/impact

7.1.3.1. Randomization

Randomization of study participants is important to avoid the caregiver consciously or unconsciously distributing TripleA treatment to a certain category of patients. The patient population is heterogeneous, but demographic and social differences between the study arms should be due to chance and not other factors. The randomization takes place according to the principle of permuted blocks in order to distribute the patients as far as possible so that the individual therapists do not treat only one study arm. Each caregiver will have access to their own randomization list. See also section 8.8.2.

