9.1.2.2. Secondary efficacy endpoints

- i) Change in total amount of alcohol consumed per 4-week period after 6 months from "baseline." An ANOVA model for repeated measurements will be used to compare the groups.
- ii) Change in total amount of alcohol consumed per 4-week period after 12 months from "baseline." An ANOVA model for repeated measurements will be used to compare the groups.
- iii) Proportion of completely sober patients at 12 months A logistic regression model will be used to compare the groups.
- iv) Proportion of completely sober patients at 6 months. A logistic regression model will be used to compare the groups.
- v) Change from baseline in the number of heavy drink days per 4-week period at 6 and 12 months, respectively. An ANOVA model for repeated measurements will be used to compare the groups.
- vi) Change from "baseline" in the number of non-drinking days per 4-week period at 6 and 12 months, respectively. An ANOVA model for repeated measurements will be used to compare the groups. Förändring från "baseline" i antalet standardglas per dryckesdag per 4-veckorsperiod vid 6 och 12 månader, respektive. vii) Time to relapse (ie first alcohol intake). For

patients with the goal of becoming alcohol-free, relapse is defined as the first day after "baseline" where alcohol consumption was found, while relapse for patients with the goal of reducing alcohol consumption is defined as the first day after "baseline" where heavy alcohol consumption is found. Heavy consumption is defined for women as a day with 4 or more glasses, while for men it is defined as a day with 5 or more glasses. The data sources TripleA, TLFB or blood samples are used to detect recurrence. To compare the survival curves, ie. the variable time to recurrence, between the treatment groups a log-rank test will be used.

- vii) CGI improvement. The proportion of respondents at follow-up visits is compared between the groups with a logistic regression model.
- viii) EQ-5D. The groups are compared regarding change from "baseline" with ANOVA model. No significant difference is expected, as quality of life forms are generally not particularly sensitive to change after treatment.
- ix) Participation in treatment. To compare the survival curves, ie. the variable time until the treatment is stopped, between the treatment groups a log-rank test will be used.

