- x) Compliance with TripleA. The proportion of measurements performed by those announced is calculated and reported for the TripleA arm.
- xi) Compliance with the agreed plan for visits to the care provider and / or visits to AA meetings. The treatment groups are compared with respect to the proportion of visits performed based on CRF data with a logistic regression model. For the TripleA arm, the corresponding data collected via TripleA and the correspondence between TripleA and CRF data are also evaluated.
- xii) Alcohol metabolites in the blood. Changes from baseline to 6 and 12 months, respectively, in PEth and CDT levels are calculated and the treatment groups are compared with an ANOVA model for repeated measurements.
- xiii) Evaluation of AUDIT data. The treatment arms will be compared with respect to:
 - xiv) - The proportion of patients who after 12 months have lowered their AUDIT score
 - xv) - The proportion of patients who after 12 months have lowered their AUDIT score to at least one zone
 - xvi) - Proportion of patients who after 12 months have a risk level <II (i.e. less than 6 AUDIT points for women, 8 AUDIT points for men).
- xvii) Evaluation of the number of "reds" and the number of missing blows in TripleA.

TripleA generates new types of high-resolution data that need to be handled in this and future clinical trials. In the simple case, the patient performs all agreed alcohol tests. For these, we can easily calculate the frequency of negative and positive alcohol tests in relation to a limit value for alcohol in the exhaled air. A fully sober patient has then probably performed 90 (3 / day) negative alcohol tests for 30 days in a month and can be considered 100% sober. A positive alcohol test ($> 0.1 \text{ mg / ml} = 0.2 \%$) gives a sobriety that is $1/90 = \sim 99\%$ or if it is calculated per day it will be 96.6% (29/30). What can be more complicated is to correlate this new type of high-resolution data with e.g. the number of days with large consumption from

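### The efficacy models do not specify therapist, which is the randomisation stratum, or the baseline value of the outcome; the cost is lost precision, not an invalid test

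*Combined protocol and SAP*

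**What the plan says.** **Randomisation.** Section 7.1.3.1 uses permuted blocks and adds "Each caregiver will have access to their own randomization list". Section 7.8.11 gives the motive: "it is conceivable that it matters which therapist you meet". Therapist is therefore the stratum of the design.

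**Primary model.** Section 9.1.2.1 says only "Proportion of patients who do not have heavy drinking days. A logistic regression model will be used to compare the groups". Covariates appear in one general sentence in section 9.1.1: "Factors such as gender, severity of addiction, motivation, form of therapy and socio-economic factors will be considered as covariates in the statistical analyzes". Section 7.8.11 instead assigns severity to exploratory work, in the sentence that ends "possible impact of demographic and social factors on the result will also be taken into account with exploratory analyzes".

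**Continuous endpoints.** Section 9.1.2.2 defines total alcohol, heavy drinking days and non-drinking days as change from baseline, and for each says "An ANOVA model for repeated measurements will be used to compare the groups". For PEth and CDT, changes are calculated and "the treatment groups are compared with an ANOVA model for repeated measurements". A baseline covariate is not mentioned. The log-rank tests in the same section have no stratification stated.

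**Size.** Section 9.2 assumes 30% without heavy drinking days in the control arm and a 30-point difference. It derives 42 per group for 80% power (two-sided 5%) and, with 20% dropout, 106 randomised. Missing values are handled by multiple imputation.

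**The concern.** A factor that was balanced by design because it may affect outcome would normally enter the analysis; otherwise the balance earns no gain in precision. Baseline heavy drinking days are the same measure as the endpoint, taken earlier, and so are a natural candidate for the strongest predictor available. Subtracting baseline, as the change-score analyses do, is less efficient than adjusting for it unless baseline and follow-up are almost perfectly correlated.

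There is also a question of commitment. The covariate sentence is open-ended and says only that factors will be considered, while section 7.8.11 treats some of the same factors as exploratory. A reader cannot tell which terms, if any, belong to the confirmatory test. The trial is open-label, so it is worth settling this before the data are reviewed.

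At stake are some power on the primary endpoint and a larger share of precision on the continuous endpoints.

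**Working it through.** **1. The plan's own figure.** Inputs from section 9.2: p0 = 0.30, p1 = 0.60, two-sided 5%, 80% power. The pooled rate is 0.45.

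n = [1.960 × √(2 × 0.45 × 0.55) + 0.842 × √(0.30 × 0.70 + 0.60 × 0.40)]² / 0.30² = 41.97, so 42 per group. Then 42 / 0.80 = 52.5, so 53 per group and 106 in total. Both figures reproduce.

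**2. Room in the model.** 84 evaluable patients × 0.45 = 37.8, so about 38 would have the outcome. That supports only a short list of terms.

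**3. Power for the primary endpoint.** The documents give neither prognostic strengths, number of caregivers nor block size, so all are assumed: 84 patients, blocks of 4 per list, and 6 unequal lists (22/18/14/12/10/8) or 10 lists of 8–9. Each setting is the baseline log-odds ratio per SD / therapist SD on the log-odds scale. There were 3000 trials per setting (about ±1.4 points), with likelihood-ratio tests.

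| Setting | 6 lists: unadjusted → baseline + random therapist | 10 lists: same |
|---|---|---|
| 0 / 0 | 82.2 → 81.4% (-0.8) | 82.3 → 81.2% (-1.1) |
| 0.4 / 0.3 | 83.7 → 83.8% (+0.1) | 83.0 → 82.8% (-0.2) |
| 0.8 / 0.5 | 82.7 → 86.4% (+3.7) | 81.4 → 86.1% (+4.7) |
| 1.2 / 0.8 | 82.9 → 91.1% (+8.2) | 83.4 → 90.8% (+7.4) |

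Most of the gain comes from baseline. With baseline alone (6 lists, 5000 trials) the changes are -1.3, 0.0, +2.8 and +6.0 points. A separate simulation with 5 therapists and fixed therapist terms also ranged from -0.6 (83.0 → 82.4%) to +7.9 (84.3 → 92.2%).

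**4. Type I error**, at 30% and at 45% in both arms, over the same settings:

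- Unadjusted: 4.3–6.9%; 4.0–4.6% at therapist SD 1.0, so slightly conservative when therapist matters strongly.
- Baseline plus random intercept: 5.2–6.4%.
- Cochran-Mantel-Haenszel stratified by list, without baseline: 4.2–6.1%.
- Baseline plus fixed therapist terms: 5.4–5.9% with 3 lists, 5.3–6.8% with 6, 5.9–8.1% with 10.

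The upper unadjusted values reflect a discrete test at this size, not the omitted terms. Summing the two Binomial(42, p) distributions over all tables with a likelihood-ratio statistic above 3.84 gives 5.1% at p = 0.30 and 6.2% at p = 0.45, with no covariate involved.

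At the 0.8/0.5 setting, fixed therapist terms added no power beyond baseline once size was equalised: 85.3% (baseline only) against 84.5% with 6 lists, and 85.2% against 84.6% with 10.

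**5. Continuous endpoints.** With equal variances at baseline and follow-up, and correlation ρ, the variances relative to follow-up alone are 2(1 - ρ) for the change score and 1 - ρ² for ANCOVA. The ratio is (1 - ρ²) / [2(1 - ρ)] = (1 + ρ)/2:

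- ρ = 0.3: 0.65, or 35% lower with ANCOVA
- ρ = 0.5: 0.75, or 25% lower
- ρ = 0.7: 0.85, or 15% lower

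**The case against.** The strongest reply is that nothing here is an error. Balance by therapist is achieved by design, the unadjusted logistic test is valid, and the sample size is right for it. The sentence in section 9.1.1 is open-ended, so therapist and baseline drinking are unspecified rather than excluded, and severity of addiction is undefined and could be taken to include baseline drinking. Every prognostic strength above is assumed, and at the weak setting the gain is nil. Therapist terms also carry a risk of their own: as fixed effects over many small lists they inflate type I error.

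All of that stands, and it fixes the size of the point: an improvement in precision and specification. It does not remove it, because an open list that section 7.8.11 partly contradicts does not settle the primary model.

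Two stronger readings are not supported. First, a reader might infer that the patient's self-confidence, which section 7.3.4 calls predictive, has been left out. The plan uses motivation as the label for the whole Appendix F questionnaire, which contains that question, so section 9.1.1 reasonably covers it. Second, a reader might infer that listing form of therapy as a covariate means adjusting for something that changes after randomisation. Therapy is recorded at every visit (7.3.9) and may change after a relapse (7.8.3.3). But it is also documented at visit 1, listed before randomisation (7.8.2), and section 7.8.11 treats it as background treatment: "Descriptive statistics will be presented for what the distribution of treatment methods looks like in the various treatment arms". That is a missing time point, not a planned biased analysis.

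**Conclusion.** The point holds as a recommended improvement. No efficacy model specifies the randomisation stratum, the primary model does not specify the baseline value of its own outcome measure, and the change-from-baseline ANOVAs state no baseline covariate. The cost is precision: about -1 to +8 power points on the primary endpoint, depending on assumed strengths, and 15–35% of variance on continuous endpoints for correlations of 0.7 down to 0.3 with equal variances. Part of the power gain may reflect the random-intercept test's size of 5.2–6.4%. Multiple imputation was not simulated. Glasses per drinking day and SADD change have no stated model, so the change-score point cannot be checked for them.

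A reader might go further and infer that the primary test is invalid or the trial undersized. The reproduced sample size and the unadjusted error rates do not support that. Nor do the documents show that the open covariate list would be used to choose a favourable model; closing it simply removes the question.

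**What to change.** - **Primary model:** logistic regression with arm, baseline number of heavy drinking days, and therapist as a random intercept. Alternatively, use an analysis stratified by list, with small lists pooled by a rule set before data review. Do not use fixed therapist terms if there are many small lists.
- **Covariate list:** close it for the primary model, align sections 9.1.1 and 7.8.11, and use the same terms in the imputation model of section 9.2.
- **Continuous endpoints:** enter the baseline value as a covariate (ANCOVA or a mixed model) in place of ANOVA on change.
- **Clarification only:** limit covariates to values recorded before the allocation envelope is opened. Code form of therapy as undecided where it is not yet chosen at visit 1, and keep later therapy descriptive or exploratory, as section 7.8.11 plans.

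This is a change of wording with no new data collection: baseline drinking is recorded at visit 1 and the list identifies the therapist. The costs are about 1–2 power points if neither term is prognostic, a type I error of about 5–6% with the random intercept, and possible pooling of small lists. The stated sample size need not change.
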